## **Applicable Analysis Methods**

Measurement error or bias for the kth sample e(k) is defined as

$$e(k) = rSO_2(k) - SavO_2(k)$$
.

Mean bias over N data points is defined as

$$\mu = \frac{1}{N} \sum_{k=1}^{N} e(k)$$

The Arms can be calculated as

$$A_{rms} \approx \sqrt{\mu^2 + s^2}$$

where s is the estimated standard deviation of bias, accounting for within-subject correlation, which is calculated using the Bland and Altman method for repeated measures. The 95% confidence interval of mean bias was calculated as  $(\mu - 2s/\sqrt{N})$ .

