- This is a prospective, clinical observational study in pediatric patients with heart disease to collect cerebral recordings of an investigational device sensor (Masimo O3™ regional oximetry system) placed on the subject's forehead as well as oxygen saturation values from arterial blood samples and jugular bulb blood samples for the development and evaluation of algorithms Parental or legal guardian consent and where possible subject assent will be obtained to act as a Human Research Subject prior to being enrolled in the study.
- Demographic information and medical history will be obtained for each enrolled subject prior to the start of the procedure.

An optical finger pulse oximeter sensor to measure SpO2, PI and PR will be placed for continuous monitoring throughout the procedure.

- One or two (depending on size of forehead) Masimo O3[™] cerebral oximetry sensors will be placed on the subjects forehead, then connected to a Masimo Root bedside monitor through a Masimo O3[™] module.
- A laptop with software will be connected to the Root bedside monitor for continuous data collection of all O3 and Masimo SET parameters (SpO2, PR, PI).
- A cardiac catheterization procedure will be performed following institutions standard of care.
- The cardiac interventionist will begin the catheterization process as per standard of care and obtain arterial and venous access. The venous catheter tip will be directed towards the jugular bulb and its correct localization confirmed by fluoroscopy.

samples will be placed in ice and analyzed as soon as possible. The rest of the catheterization procedure will be as per standard of care.

At the conclusion of the study devices and data recording will be stopped,

and study sensors will be removed.

 Subjects will be followed 48 hrs. after the procedure with a phone call to assess any study related adverse event

Subjects

Enrollment will not exceed 50 subjects. This sample size is expected to be sufficient for algorithm development and validation.

Inclusion criteria

- Pediatric patients undergoing cardiac cathetheterization procedure for treatment or diagnosis of cardiovascular disease
- 1 day to less than 18 yrs. of age
- Weight between 3.5 and 40 kg
- parental or legal guardian consent and subject assent

Exclusion criteria

- Failure to obtain written consent
- Equal or more than 18 years in age
- Weigh more than 40 kg or less than 3.5 kg
- Jaundice with bilirubin levels higher than the reference range

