## **Data Analysis**

We compute error statistics, including mean bias, precision, standard deviation of bias, and absolute root-mean-squared-error accuracy  $A_{rms}$ , accounting for within-subject correlations.

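### The SAP says mean bias accounts for within-subject correlation, but its formula is a plain average and its interval uses s/√N over readings, so the interval is too narrow when children give several correlated readings.

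*SAP*

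**What the plan says.** The SAP's Data Analysis section reads "We compute error statistics, including mean bias, precision, standard deviation of bias, and absolute root-mean-squared-error accuracy" and closes that sentence with "accounting for within-subject correlations". Grammatically, the closing phrase covers mean bias as well as the spread and A_rms.

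Applicable Analysis Methods then gives the formulas:

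- The error: "Measurement error or bias for the kth sample e(k) is defined as" the O3 reading minus the blood reference.
- The mean: "Mean bias over N data points is defined as" (1/N) times the sum of the errors. There is no subject index, weight or model.
- The spread: A_rms is √(μ² + s²), with s taken from the Bland–Altman repeated-measures approach. This is the one formula in which clustering is handled.
- The interval: "The 95% confidence interval of mean bias was calculated as" μ minus 2s/√N. Only one limit is legible; I read it as the lower limit of a two-sided interval. N is the number of data points.

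In the Protocol, the Procedure section says of the forehead sensors: "One or two (depending on size of forehead", so the number of sensors can differ between children. The Subjects section says "Enrollment will not exceed 50 subjects". The text available for review does not say how many blood draws each child gives, or whether two sensors on one draw give one error value or two.

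**The concern.** Only s is adjusted for clustering. Dividing it by √N treats N readings as N independent pieces of information. Readings from one child share that child's own offset, so the information on mean bias lies between the number of children and the number of readings. The SAP interval would then claim more precision than the data hold, in a study whose purpose is to calibrate and validate the device.

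The second issue is weighting. In the SAP average a child with m readings has weight m/N. If each sensor supplies its own error value, weight follows forehead size, in a study that admits children from 3.5 to 40 kg. If bias also varied with size, the pooled mean would move toward the children with two sensors. The documents give no figure on whether it does.

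**Working it through.** The plan states no paediatric variance, sample-size calculation or result, so there is no figure of its own to reproduce. The check compares the SAP rule with the clustered variance under stated assumptions.

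**Inputs**

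- Children: 50, the Protocol's cap.
- Total SD: the adult figures in the Protocol's Background are bias 0.4 and A_rms 4.0, so s² = 4.0² − 0.4² = 15.84 and s = 3.98.
- Within-child SD: 2.1, the adult trending accuracy. Treating it as a within-subject SD is an assumption; the Protocol does not define it that way.
- Hence within-child variance vw = 2.1² = 4.41, between-child variance vb = 15.84 − 4.41 = 11.43 (SD 3.38), and ICC = 11.43/15.84 = 0.72.
- Readings (assumed): 25 children with one and 25 with two. N = 75 and Σm² = 25×1 + 25×4 = 125.

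**Standard error and coverage**

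- SAP rule: √(15.84/75) = 0.46.
- Variance of the pooled mean: vb·Σm²/N² + vw/N = 11.43×125/5625 + 4.41/75 = 0.254 + 0.059 = 0.313. SE = 0.56.
- Coverage of μ ± 2s/√N: 2Φ(2×0.46/0.56) − 1, about 90%. The nominal value with multiplier 2 is 95.4%.

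Coverage over a range of ICCs, again with 50 children:

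| Readings per child | ICC 0 | ICC 0.3 | ICC 0.5 | ICC 0.8 |
|---|---|---|---|---|
| All 1 | 95.4% | 95.4% | 95.4% | 95.4% |
| 25 with 1, 25 with 2 | 95.4% | 93.2% | 91.7% | 89.4% |
| All 2 | 95.4% | 92.1% | 89.8% | 86.4% |
| All 4 | 95.4% | 85.3% | 79.4% | 72.2% |

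The interval fails even when every child gives the same number of readings, provided that number exceeds one and the ICC is above zero.

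**Precision of the point estimate, same split, ICC 0.72**

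- Optimal variance: 1/Σ[1/(vb + vw/m)] = 1/[25/15.84 + 25/13.635] = 0.293, SE 0.54.
- Ratio: 0.313/0.293 = 1.07, so the pooled mean has about 7% more variance.

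**Weighting**

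- Share of the two-reading group in the pooled mean: 50/75 = 66.7%, against 50% if each child counts once.
- Shift: 0.667 − 0.500 = 0.17 point per 1-point difference in bias between the groups.
- The random-intercept model gives that group (1/13.635)/(1/13.635 + 1/15.84) = 53.7%, so the pooled mean differs from the model estimate by about 0.13 point per 1-point difference.
- With equal counts the shift is zero.

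**Reading count unrelated to error.** In a simulation with true bias 0.4, one, two or four readings per child and ICC 0.5, the pooled mean averaged 0.406 and the per-child mean 0.405, with SDs of 0.52 and 0.50.

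**The case against.** The strongest reply is that accounting for correlation concerns variance, not the point estimate. A plain mean beside a clustered s is coherent, and weighting by reading or by child is a choice of estimand. This stands for the point estimate: if reading count is unrelated to error, both are unbiased. It does not rescue the interval. The variance that matters there is that of the mean, and s/√N leaves the clustering out of it.

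Three stronger readings are tempting, and the documents do not support them.

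- **Some children dominate the mean.** The only visible source of unequal counts is one sensor or two, a weight ratio of at most 2:1. In the 25/25 split that is 2.7% against 1.3% per child. Even this needs each sensor to give its own error value; the SAP indexes errors by sample, which could mean one value per blood draw.
- **Children differ in number of draws.** The sampling step in the Protocol's Procedure section is cut off in the available text, and part of the SAP was not available. A fixed number may have been stated there, so unequal draws cannot be charged to the plan.
- **A subject-level mean would reveal bias in the smallest children.** It would not. One overall figure can hide opposite biases in small and large children whichever way it is weighted.

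The effect on A_rms is also small. With s held at 3.98, moving μ from −0.2 to +1.0 takes A_rms only from 3.99 to 4.10.

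**Conclusion.** The point holds for the interval and, more modestly, for the mean. The SAP promises an adjustment for mean bias that neither the formula for the mean nor its standard error carries.

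Under the assumed ICC of 0.72 and the 25/25 split, the SAP rule understates the standard error by about 18% (0.46 against 0.56), and a nominal 95% interval covers about 90%. The shortfall grows with readings per child and with the ICC, and disappears if each child gives one reading or the ICC is zero.

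The loss of precision (about 7% in variance) and the shift of 0.17 point per 1-point difference in bias arise only if counts differ; the shift also needs bias to differ between the groups. The sizes rest on adult variance figures, on reading the adult trending accuracy as a within-subject SD, and on an assumed distribution of readings. The direction of the interval error needs only repeated, positively correlated readings within children.

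**What to change.** In Applicable Analysis Methods, estimate mean bias and its 95% confidence interval from a random-intercept model for the errors with subject as random effect, replacing μ ± 2s/√N. Report the average over N readings beside it, labelled as such. State whether two sensors on one blood sample give one error value or two, and so how N is counted.

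The cost is one model fit on data already collected and a wider interval: in the worked split the SE is 0.54 instead of 0.46, or about 0.16 point on each side with a multiplier of 2. The headline mean is then no longer the simple average over readings, which is why both should be shown.

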The O3 regional oximetry sensors contain a 4-wavelength LED emitter, and two light detectors for the detection of deep tissue and superficial oxygenation. The system is designed to allow the near-infrared light to superficially penetrate the scalp, skull and brain tissue. Using multiple wavelengths of light and spatially distributed photo-detectors to interrogate the deep tissue, the O3 system measures regional saturation of oxygen (rSO_2) by establishing a relationship between the light absorbed by the tissue and its oxygen saturation.

The accuracy validation study for the O3 system in an adult population reported a mean bias of 0.4%, absolute root-mean-squared accuracy of 4.0% and trending root-mean-squared accuracy of 2.1%. These accuracy statistics are significantly better than the test accuracy of the most commonly used regional oximeter (INVOS) and match the accuracy of the laser-based Foresight system. The O3 system is much more compact system, technology packed in a small POD.

Finally, the Masimo O3 POD connects to the standard bedside monitor (recently released as Masimo Root that allows simultaneous connection and monitoring of other clinical parameters, including all RainbowSET parameters, SEDLine, Respiration rate, etc., and is configured to connect to 3rd party devices as well).

During data collection, in additional to arterial and venous blood oxygen saturation, other relevant hemodynamic information needs to be recorded. A shift in cerebral vascular tone may change the ratio of arterial to venous blood in the light path.

Because changes in arterial carbon dioxide content are known to change cerebral vascular tone, pH and PCO₂ will be measured and recorded on each blood sample analysis.

LOCATION

The pediatric cardiac catheterization laboratory at Stanford University Medical Center

EQUIPMENT AND MATERIALS

Hospital Standard of Care equipment will be used for the catheterization procedure. In addition the following study specific equipment will be used and supplied by Masimo Corp.

- Masimo O3TM regional oximetry device with forehead sensors and O3TM modules
- Masimo Root Pulse CO-Oximeter and disposable Masimo SET optical sensors Laboratory co-oximeter and blood gas analyzer for determination of arterial (SaO_2) and venous (SvO_2-) and blood gases for pH, pCo2 and PO2

PROCEDURE

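### The 95% interval for mean bias uses the square root of the number of data points, so it is too narrow when children contribute repeated, correlated readings

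*SAP*

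**What the plan says.** The SAP's Data Analysis section says the error statistics are computed "accounting for within-subject correlations". Under Applicable Analysis Methods, the average error is introduced with "Mean bias over N data points is defined as", so N counts individual measurements, not children. The standard deviation s is described as "accounting for within-subject correlation, which is calculated using the Bland and Altman method for repeated measures". The section ends with "The 95% confidence interval of mean bias was calculated as" a limit of the form μ − 2s/√N. Only the lower limit is legible. I read the interval as μ ± 2s/√N and do not count the missing upper limit as an error.

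The Protocol adds two relevant facts. Its Subjects section says "Enrollment will not exceed 50 subjects". Its Procedure section allows either one or two forehead sensors per child. The readable text does not give the number of blood draws per child, a value for the within-child correlation, or whether two sensors on one child are averaged or counted separately.

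**The concern.** The repeated-measures Bland–Altman method estimates the spread of a single error, combining between-child and within-child variance. It does not supply the standard error of the overall mean. Dividing that standard deviation by the square root of the number of measurements is right only if all measurements are independent. The plan recognises within-child correlation when it estimates s, then drops it when it forms the interval.

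At stake is the only confidence interval in the readable SAP, in a study meant to calibrate and validate the device. Computed as written, it can make the mean bias look more precisely known than it is.

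**Working it through.** **Inputs**
- Multiplier 2, N = data points, s = repeated-measures SD: SAP, Applicable Analysis Methods.
- At most 50 children: Protocol, Subjects. This is a ceiling, not a planned analysis number.
- Readings per child (m) and ICC: not in the readable text. Assumed m of 1, 2 and 4, and ICC from 0 to 0.5.
- s, for illustrating width only: the Protocol's Background reports an adult bias of 0.4% and "absolute root-mean-squared accuracy of 4.0"%. The SAP's own relation A_rms² = μ² + s² gives s = √(4.0² − 0.4²) = 3.98, taken as 4. This is not a pediatric value.

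**Step 1: reproduce the stated level.** With independent errors, coverage of μ ± 2s/√N is 2Φ(2) − 1 = 95.4%. Using 2 in place of 1.96 is ordinary rounding, so the formula delivers its label under independence.

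**Step 2: variance of the mean with repeated readings.** Let child i give m_i readings, with between-child variance sb² and within-child variance sw², so that s² = sb² + sw² and ICC = sb²/s². Then

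Var(μ) = sb²·Σm_i²/N² + sw²/N = (s²/N)·DE, with DE = 1 + ICC·(Σm_i²/N − 1).

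For equal m this is DE = 1 + (m − 1)·ICC. The SAP formula omits DE, so the interval is too narrow by √DE and its coverage is 2Φ(2/√DE) − 1.

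**Step 3: numbers.** The simulated columns use 50 children, 20,000 runs and s from the Bland–Altman variance components. The last column is the interval proposed under the fix.

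| Readings per child | ICC | DE | √DE | Coverage, formula | Simulated, SAP interval | Simulated, proposed interval |
|---|---|---|---|---|---|---|
| 2 | 0 | 1.00 | 1.00 | 95.4% | 95.6% | 96.2% |
| 2 | 0.1 | 1.10 | 1.05 | 94.3% | 94.4% | 95.5% |
| 2 | 0.2 | 1.20 | 1.10 | 93.2% | 93.0% | 95.1% |
| 2 | 0.5 | 1.50 | 1.22 | 89.8% | 89.3% | 95.1% |
| 4 | 0.2 | 1.60 | 1.26 | 88.6% | 88.2% | 94.9% |
| 4 | 0.5 | 2.50 | 1.58 | 79.4% | 78.5% | 94.8% |
| 25 children with 1, 25 with 3 | 0.2 | 1.30 | 1.14 | 92.1% | 91.9% | 95.0% |
| 25 children with 1, 25 with 3 | 0.5 | 1.75 | 1.32 | 86.9% | 86.2% | 94.7% |

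For the unequal case, N = 25·1 + 25·3 = 100 and Σm_i² = 25·1 + 25·9 = 250, so DE = 1 + 1.5·ICC. The average is 2 readings per child, yet the loss exceeds that for an even 2 each. Formula and simulation agree within one percentage point. A separate simulation with 40,000 runs gave 89.1% at m = 2, ICC 0.5 and 79.5% at m = 4, ICC 0.5.

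**Step 4: does s absorb the missing factor?** No. In the 40,000-run simulation the estimated s was 1.00 to 1.02 times the true total SD whenever ICC was 0.1 or more.

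**Step 5: width in saturation points** (50 children, s = 4, t on 49 degrees of freedom = 2.01).
- m = 2, ICC 0.2: SAP 2·4/√100 = 0.80; corrected 2.01·4·√(1.2/100) = 0.88.
- m = 4, ICC 0.5: SAP 2·4/√200 = 0.57; corrected 2.01·4·√(2.5/200) = 0.90.

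**The case against.** The algebra is not in dispute; the case against is about occurrence and consequence.

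- **Unknown inputs.** The readable text gives neither m nor ICC, and with one reading per child or zero correlation nothing is lost. This stands as a limit on the size. It does not rescue the formula: a repeated-measures method is needed only if some children give more than one reading, and the formula is wrong whenever those readings are positively correlated. A positive ICC is plausible but not stated.
- **Slack from the multiplier 2.** Coverage falls below 95% only when DE exceeds (2/1.96)² = 1.041, which means ICC above about 0.041 at m = 2 or 0.014 at m = 4. True, but negligible in practice.
- **No promise about the interval.** The Data Analysis section lists bias, precision, SD and A_rms as the statistics adjusted for correlation, and does not name the interval. That weakens any charge of outright contradiction. It does not make the standard error correct.
- **Little depends on it.** No acceptance limit, test or decision rule in the readable text uses the interval, and the illustrated widening is 0.08 to 0.33 saturation points (0.88 − 0.80 and 0.90 − 0.57) against a single-reading SD of 4. This stands and limits the importance of the point.
- **Two sensors.** Nothing readable shows that both sensors enter N. This stands: it is a possible second source of repeated readings, and the conclusion does not rest on it.

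**Conclusion.** The interval is wrong as written for the repeated-measures setting the SAP itself provides for. It is too narrow by √DE. Over the assumed values with correlated readings, true coverage runs from 94.3% (m = 2, ICC 0.1) to 79.4% (m = 4, ICC 0.5, the upper end of the assumptions). The direction and the formula are certain given more than one reading per child and ICC above zero; the actual size cannot be fixed from the readable text. The damage is confined to this interval: the point estimates of mean bias, s and A_rms do not change. It should be fixed, but it does not threaten the study's main accuracy figures.

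**What to change.** Replace s/√N with a standard error that respects the child as the unit:

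SE² = sb²·Σm_i²/N² + sw²/N,

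using the variance components the Bland–Altman method already produces, and report μ − t·SE to μ + t·SE with t on (number of children − 1) degrees of freedom. A bootstrap that resamples whole children is an acceptable alternative. State what counts as one data point, including how two sensors on the same child are handled, and report both the number of children and the number of data points beside the interval.

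The cost is one formula and a sentence or two in the SAP, with no new data. The interval widens when ICC is above zero. If the correlation proves negligible it will hardly change: simulated coverage of the proposed interval at m = 2, ICC 0 was 96.2%, slightly conservative.
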